11.1.4 Mean Bisacodyl dose per week

The mean bisacodyl dose per week (mg) will be calculated as

(sum of bisacodyl doses (mg) during the period of interest/number of days in the period of interest) x 7.

The mean bisacodyl dose per week (mg) will be assessed for the following time intervals (NKTR-118 group only): randomization to Month 1, Months 1 to 3, Months 3 to 6, Months 6 to 9, and Months 9 to 12.

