Unless there is a need for urgent intervention, NKTR-118 patients will not be allowed to take any medication for treatment of constipation, other than bisacodyl, during the course of the study without the prior agreement of the investigator. If after a minimum of 72 hours, a NKTR-118 patient has not experienced a BM, he/she may take bisacodyl rescue therapy (10 to 15 mg dose, ie, 2 to 3 bisacodyl tablets at a time). If the patient remains constipated, bisacodyl rescue therapy may be repeated up to 2 additional times, as necessary, each 10 to 15 mg dose separated by 12 hour intervals. It is recommended that the bisacodyl tablets be taken either at bedtime or before breakfast. If after 3 doses of bisacodyl rescue therapy, the patient still has not experienced a BM, the investigator may prescribe one-time use of an enema. The timing of administration of this therapy should be noted in the home diary. In addition, the site is to record any enema prescription on the enema eCRF. If these secondary interventions fail, the patient should be discontinued from the study and referred for additional medical evaluation. Since the patient is discontinued from the study, the investigator should recommend initiation of any therapy deemed most appropriate.

Throughout the study, investigators will be encouraged to maintain the patient's baseline pain control regimen. If there is a need to control pain, investigators should manage pain per the guidelines provided in the study reference manual with dose adjustments made as needed in accordance with the patient's clinical needs. Concomitant non-opioid analgesics will not be prohibited, but investigators will be encouraged to maintain such drugs at stable doses on-study, if possible.

It is preferred that the investigator manage the patient's opioid medication during the study; however, it is recognized that pain may be managed by a health care provider outside the study. In such cases, communication between the patient's personal physician and the investigator is strongly encouraged. Although it is desirable that patients be maintained on a stable opioid regimen during the study, should changes in the maintenance opioid regimen be necessary they should be reported to the site at the next study visit and recorded on the

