5.2.1 Procedures for randomization

Randomization codes will be distributed and communicated to study sites by use of an IVRS.

Eligible patients will be randomized to receive NKTR-118 25 mg or Usual Care in a 2:1 ratio. The actual treatment assigned to individual patients will be determined by a randomization scheme that has been loaded into the IVRS database. The randomization scheme will be produced by a computer software program called GRand (AstraZeneca’s Global Randomization system). If a patient is discontinued from the study, his/her patient number or enrollment number will not be reused, and the patient will not be allowed to re-enter the study. Randomized patients who discontinue early from the study will not be replaced.

If a randomization number is allocated incorrectly, no attempt should be made to remedy the error once the IP has been dispensed. The patient will continue with the allocated number and IP. AstraZeneca or its representative should be notified as soon as the error is discovered. Subsequent patients will continue using the first unallocated randomization number in the original numbering sequence.

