Unless there is a need for urgent intervention, NKTR-118 patients will not be allowed to take any additional medication for treatment of constipation, other than bisacodyl, during the course of the study without the prior agreement of the investigator. This includes over-the-counter treatments for constipation.

NKTR-118 patients will be instructed on the guidelines for rescue bisacodyl use noted above. If these secondary interventions fail, the patient should be discontinued from the study and referred for additional medical evaluation. Since the patient is discontinued from the study, the investigator should recommend initiation of any therapy deemed most appropriate.

NKTR-118 patients will be asked to return unused bisacodyl at each visit during the treatment period. Bisacodyl use will be reviewed with the patient at each visit and recorded on the bisacodyl drug accountability eCRF.

Usual Care treatment arm

Patients in the Usual Care treatment group will have their constipation managed by the investigator according to his/her best clinical judgment (see Section 5.5.2.2). The investigator may choose from a broad range of laxatives (see below). However, peripheral μ -opioid antagonists, such as methylnaltrexone and naloxone containing products, are not allowed (see Section 5.6.3). Patients assigned to Usual Care treatment will not be permitted to take any medication for treatment of constipation other than that prescribed by the PI, without the prior agreement of the PI. No specific rescue laxative protocol is determined for patients randomized to receive Usual Care. Usual care laxative medication will be reviewed with the patient at each visit and recorded on the laxative medication eCRF. This includes bisacodyl if the patient received this medication.

All patients

The following laxative medications are prohibited on-study for patients who receive NKTR-118. These medications do not constitute an exhaustive list of prohibited laxatives. These laxative medications are permitted for patients in the Usual Care arm if prescribed by the investigator as part of their OIC treatment:

- Milk of magnesia or magnesium citrate
- Non-absorbable phosphate
- Cascara

- Senna
- Castor oil/mineral oil
- Epsom salt
- Lactulose
- Polyethylene glycol
- Docusate
- Enemas
- Tegaserod
- Lubiprostone (Amitiza[®])
- Drugs blocking fat absorption with an associated laxative effect
- Prucalopride
- Prune juice
- Herbal preparations for constipation

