5.8 Discontinuation from study

Patients are at any time free to discontinue from the study (IP and assessments), without prejudice to further treatment (withdrawal of consent). Such patients will always be asked about the reason(s) and the presence of any AEs. If possible, they will be seen and assessed by an investigator and Visit R15 assessments will be performed. Adverse events will be followed up (see Sections 6.3.4 and 6.3.5); and all study drugs should be returned by the patient.

Discontinued patients will not be replaced.

Patients should be discontinued in the following situations:

- Patient decision. The patient is at any time free to discontinue treatment, without prejudice to further treatment.
- Inadequate pain control after reasonable attempts to control pain have been unsuccessful
- Hepatotoxicity (significantly increased elevations in liver transaminases as defined in Section 6.3.9.2. The protocol for handling patients with elevated liver transaminases including guidelines for discontinuing patients is discussed in Section 6.3.9.2).

- Severe non-compliance to the CSP (including dosing regimen with NKTR-118 or Usual Care, and/or prescribed opioid) as judged by the investigator in consultation with the study physician
- Incorrectly enrolled patients, involving increased safety risk. The investigator should consult with the study physician before discontinuing the patient unless there is a medical urgency.
- Patient is lost to follow-up.
- The patient has a clinically significant or serious AE (eg, new or worsening heart failure) or sustained clinically significant treatment emergent abnormalities in vital signs that would not be consistent with continuation in the study, as determined by the investigator, AstraZeneca, or its representative, or the patient.
- Safety reasons as judged by the investigator.
- Patient becomes pregnant.
- Significantly worsened OIC refractory to medical treatment as judged by the investigator (including failure of the laxative rescue regimen either before or after randomization)
- The patient is unable to comply with the restrictions on the use of concomitant medications as detailed in Section 5.6 (in such cases the investigator should consult with the study physician before discontinuing the patient).
- The patient is unable to tolerate the study drug.

Abdominal pain has been reported as an AE in a previous trial with NKTR-118. The management of severe abdominal pain is discussed in Section 6.3.13.2).

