11.1.3 Daily opioid dose

Opioid doses will be recorded for each patient, including both the maintenance dose and dosing for breakthrough pain. However, the daily opioid dose in morphine equivalents (mg/day) will be calculated using only the maintenance dosing information. The mean daily opioid dose (mg/day) for an interval will be calculated as the sum of daily opioid doses

(mg/day) for the interval divided by the number of days within the interval in which the data were collected. The mean daily opioid dose will be calculated for the following time intervals: randomization in this study to Month 1, Months 1 to 3, Months 3 to 6, Months 6 to 9, and Months 9 to 12. For rollover patients, the mean daily opioid dose will also be calculated for the following time intervals: randomization in the previous NKTR-118 study (D3820C00005 or D3820C00007) to Months 1, 3, 6, 9, and 12.

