12.2.1 Safety analyses

Adverse events will be coded using the MedDRA dictionary. Three sets of AE summaries will be generated: (1) all AEs recorded in the clinical database, (2) all TEAEs (as defined in Section 11.1.1), and (3) AEs occurring after the last dose of study drug.

Number of events and proportions will be tabulated by preferred term and system organ class. An event that occurred 1 or more times on the date of or subsequent to first dose of study drug will contribute 1 observation to the numerator of the proportion. The denominator of the proportion will comprise all patients in the Safety analysis set. Adverse events will also be

summarized by intensity and separately, by causality (as determined by the investigator). Should a patient experience the same preferred term/system organ class within multiple intensity or causality categories, the patient's worst occurrence (most severe/most related) will be retained in the tabulations. Serious AEs and commonly occurring AEs will be summarized in a generally similar manner. Adverse events of special interest may be further summarized and analysis of AEs occurring within specific time periods (e.g. after 3 months, after 6 months, etc.) may be considered.

Adverse events, SAEs, AEs leading to death, and AEs leading to study discontinuation will be tabulated for each treatment group. Descriptive statistics for time to onset and duration of select AEs may be summarized by treatment group. Adverse events that could potentially be indicative of centrally mediated opioid withdrawal, abuse potential, and bowel perforation will be identified prior to database lock and will also be summarized by each treatment group.

The mean daily opioid dose will be summarized for the following intervals: randomization to Month 1, Months 1 to 3, Months 3 to 6, Months 6 to 9, and Months 9 to 12. The mean bisacodyl dose per week will be summarized only for the NKTR-118 treatment group using descriptive statistics for the following intervals: randomization to Month 1, Months 1 to 3, Months 3 to 6, Months 6 to 9, and Months 9 to 12. The observed composite modified Himmelsbach score and change from baseline will be summarized by treatment group at Week 1, Months 1, 3, 6, 9, and 12 using descriptive statistics. The observed score and change from baseline in the NRS pain scores (average in the 7 days prior to the study visit) will be summarized by treatment group for Weeks 1 and 2, Months 1, 2, 3, 6, 9, and 12.

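### Section 11.1.4 divides bisacodyl use by the days in a fixed interval, so on its plain reading the value is understated in the interval in which a patient leaves

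*Protocol*

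**What the plan says.** Section 11.1.4 computes the weekly dose as "sum of bisacodyl doses (mg) during the period of interest/number of days in the period of interest) x 7". The periods listed beneath it are "randomization to Month 1, Months 1 to 3, Months 3 to 6, Months 6 to 9, and Months 9 to 12". Nothing there ends the period at discontinuation, at the last dose or at the last tablet count.

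Section 11.1.3 takes the mean daily opioid dose over the same five intervals, but the sum is "divided by the number of days within the interval in which the data were collected". Section 11.3.1 also uses a patient-specific divisor for healthcare visits, namely the patient's days on study medication.

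The variable is named as a safety variable in Section 6.3.1. Section 12.2.1 states: "The mean bisacodyl dose per week will be summarized only for the NKTR-118 treatment group using descriptive statistics for the following intervals". It adds no rule for partial intervals.

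On early exit, Section 3.1 allows a first bisacodyl dose and says "bisacodyl rescue therapy may be repeated up to 2 additional times, as necessary, each 10 to 15 mg dose separated by 12 hour intervals". If there is still no bowel movement, the investigator may prescribe an enema once. Section 5.6.2 then says: "If these secondary interventions fail, the patient should be discontinued from the study and referred for additional medical evaluation". Section 5.8 lists the matching reason: "Significantly worsened OIC refractory to medical treatment as judged by the investigator (including failure of the laxative rescue regimen either before or after randomization". Section 5.2.1 adds: "Randomized patients who discontinue early from the study will not be replaced". Section 12.1.1 keeps everyone with at least one dose in the safety analysis set.

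**The concern.** For a patient who stops part-way through an interval, the numerator ends at exit. Read plainly, the denominator runs on to the end of the interval, so unobserved days count as days without bisacodyl.

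The error goes in one direction, towards less apparent rescue use. It can also be related to the outcome, because failure of the rescue regimen is itself a reason to leave. At stake is how the study describes the need for rescue laxative under long-term NKTR-118. Two neighbouring derivations in Section 11 tie the divisor to the patient's own days, so a programmer could reasonably take the different wording in 11.1.4 as deliberate.

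**Working it through.** The protocol gives no numerical value for this variable, so there is no figure to reproduce. The check compares two divisors.

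**Inputs**
- S, bisacodyl in one full rescue course: 3 doses of 10 to 15 mg, so 30 to 45 mg (Sections 3.1 and 5.6.2).
- D, interval length: assumed 30, 61, 91, 91 and 92 days, which sum to the 365 days of Section 5.5.2.1. The protocol gives month labels only.
- d, days observed in the interval: chosen for illustration.

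**Formulas**
- As written, read plainly: 7 × S / D.
- By days observed: 7 × S / d.
- Ratio of the first to the second: d / D. It equals 1 when the interval is completed.

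**One patient, one full course, then exit**

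| Interval | d | D | S (mg) | As written (mg/week) | Days observed (mg/week) | d/D |
|---|---|---|---|---|---|---|
| Months 3 to 6 | 14 | 91 | 45 | 45/91 × 7 = 3.5 | 45/14 × 7 = 22.5 | 0.15 |
| Months 3 to 6 | 46 | 91 | 45 | 45/91 × 7 = 3.5 | 45/46 × 7 = 6.8 | 0.51 |
| Months 3 to 6 | 91 | 91 | 45 | 3.5 | 3.5 | 1.00 |
| Randomization to Month 1 | 10 | 30 | 45 | 45/30 × 7 = 10.5 | 45/10 × 7 = 31.5 | 0.33 |

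With 30 mg instead of 45 mg, both values fall by one third and the ratio is unchanged.

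**Group mean in one interval**

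Assume that a share s of the patients who enter the interval leave during it, with exit times uniform, so that d/D averages 0.5. Let leavers use bisacodyl at k times the stayers' rate. The ratio of the reported mean to the observed-day mean is then [(1 − s) + 0.5ks] / [(1 − s) + ks].

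| s | k = 1 | k = 3 |
|---|---|---|
| 5% | 0.975 (2.5% low) | 1.025/1.10 = 0.932 (6.8% low) |
| 10% | 0.95 (5% low) | 1.05/1.20 = 0.875 (12.5% low) |
| 20% | 0.90 (10% low) | 1.10/1.40 = 0.786 (21.4% low) |
| 30% | 0.85 (15% low) | 1.15/1.60 = 0.719 (28.1% low) |

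Both s and k are assumptions; the protocol gives neither.

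**The case against.** The strongest reply is that the period of interest can mean the patient's own time within the interval, which is natural for a per-patient rate. The data collection fits that reading. Bisacodyl is counted as dispensed minus returned at each visit (Sections 3.1.2 and 5.7.1.2), and early leavers are asked back for a termination visit with the Month 12 assessments (Section 5.8), which include return of unused bisacodyl (Section 3.1.2.9). The last count therefore has its own date. Opioid dose is a daily quantity, so the wording of 11.1.3 may reflect a different data source rather than a different exit rule. Partial intervals are also often left to the analysis plan.

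Part of this stands. The phrase is open to that reading, and under it the error disappears. But 11.1.4 is not silent: it states a divisor and lists fixed intervals directly below, and no other section limits them to the patient's own days.

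Three stronger readings are tempting and are not supported:
- A reader might infer that reported rescue use is several-fold too low. The ratio of 6.5 (91/14) belongs to one chosen patient, not to an interval mean.
- A reader might infer that failing bisacodyl alone forces withdrawal. The protocol allows an enema first, and says that the patient should, not must, be discontinued if these measures fail.
- A reader might infer that this is the only measure of rescue need. Enemas are also counted among the procedures in Section 12.2.2 and recorded on their own form. It is the only stated measure of bisacodyl dose.

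**Conclusion.** The point holds as a flaw in a stated derivation. Read plainly, the divisor in 11.1.4 understates bisacodyl use in the exit interval by the factor d/D, and it differs from the rule in 11.1.3 for the same intervals.

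The reach is limited to the exit interval of patients in one arm, for a descriptive variable. No test or sample size rests on it. The group effect cannot be fixed from the protocol. It is about 2.5% to 15% too low if 5% to 30% leave uniformly within an interval with the same use as stayers, and about 7% to 28% if leavers are assumed to use three times as much. The change is worth making because the bias runs in the favourable direction and the correction is cheap.

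**What to change.** In Section 11.1.4, define the divisor as the number of days in the interval on which the patient was on NKTR-118 and covered by bisacodyl accountability. These days run from the interval start to the earlier of the interval end and the last dose or last accountability visit. Count bisacodyl over the same days. Tablet counts may not date each tablet, so the rule should say which end date governs when the last dose and the return visit differ, and apply it to numerator and denominator alike.

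Short exit intervals give unstable individual rates: 45 mg over 5 days is 45/5 × 7 = 63 mg/week. If that patient is averaged with a completer who took 45 mg over 91 days (3.5 mg/week), the unweighted mean is about 33 mg/week, whereas the pooled rate is 90/96 × 7 = 6.6 mg/week. So also report, for each interval, the group's total mg divided by its total covered days, times 7.

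The cost is one or two sentences and slightly more programming. No new data are needed, since counts at each visit and at the termination visit are already planned. The reported mean may become less favourable.

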11.1.5 Modified Himmelsbach Scale

The scores for each of 8 signs are summed to give a composite score ranging from 0 to 24 for each visit, where higher values indicate greater severity of symptoms. If more than 25% of the 8 signs are missing at a visit, the composite score will be set to missing. The composite score will be summarized at Week 1, Months 1, 3, 6, 9, and 12. Changes from baseline to Week 1, Months 1, 3, 6, 9, and 12 in the modified Himmelsbach scale will be calculated as the post-baseline value minus the baseline value. Negative changes from baseline indicate improvement.

For the new patients, baseline modified Himmelsbach values will be defined as the latest non-missing value collected prior to the first dose of study drug in this study (screening, Visit S1 or Week 0, Visit R1). For patients entering the study from a previous NKTR-118 study (D3820C00005 or D3820C00007), the primary baseline modified Himmelsbach values will be defined as the latest non-missing value collected prior to the first dose of study drug in the previous pivotal study (D3820C00004 or D3820C00005) (screening, Visit 1 or Week 0, Visit 3), and supportive baseline modified Himmelsbach will be defined as the data collected at the final visit from the previous study.

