6.3.1 Safety variables

Safety variables include:

- Incidence, nature, and intensity of AEs, treatment-related AEs, SAEs, AEs leading to discontinuation, and specific safety areas of interest
- Mean daily opioid dose for Months 1, 3, 6, 9, and 12
- Mean bisacodyl dose per week for Months 1, 3, 6, 9, and 12 (NKTR-118 group only)
- Change from baseline in NRS pain score for Week 1, Week 2, Months 1, 2, 3, 6, 9, and 12.
- Observed values and change from baseline in composite score in modified Himmelsbach scale for the evaluation of centrally mediated opioid withdrawal symptoms for Week 1, Months 1, 3, 6, 9, and 12
- Changes in vital signs and physical examination
- Changes in laboratory assessments (ie, chemistry, hematology, and U/A)
- Changes in ECGs

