6.3.8 Modified Himmelsbach Scale

Patients are rated by examination for symptoms of opioid withdrawal using the modified Himmelsbach scale. The modified Himmelsbach scale will be administered by a clinician at the study site. Patients will be rated with respect to the following symptoms as observed at the time of the assessment: yawning, lacrimation, rhinorrhea, perspiration, tremor, mydriasis, piloerection, and restlessness. The signs will be quantified on a scale of 0 to 3, with 0=none, 1=mild, 2=moderate, 3=severe. ([Himmelsbach 1941](#); [Culpepper-Morgan et al 1992](#), [Webster et al 2008](#)). To ensure adequate inter-rater agreement, raters will undergo training on proper scoring using the modified Himmelsbach scale and will receive certification provided by Bracket Global. The modified Himmelsbach scale will be administered at screening, randomization, Week 1, Months 1, 3, 6, 9, and 12. Changes in this scale should generally not be reported as AEs unless standard criteria for AE reporting are otherwise met.

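### Section 11.1.5 keeps a modified Himmelsbach sum with one or two of its eight signs unrated but does not say how that score is put on the 0 to 24 scale

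*Protocol*

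**What the plan says.** Section 6.3.8 lists eight signs rated by a clinician at the site: "The signs will be quantified on a scale of 0 to 3, with 0=none, 1=mild, 2=moderate, 3=severe". Section 11.1.5 builds the composite from them: "The scores for each of 8 signs are summed to give a composite score ranging from 0 to 24 for each visit". A larger total means more marked withdrawal. The same section then fixes the treatment of missing signs: "If more than 25% of the 8 signs are missing at a visit, the composite score will be set to missing".

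Change is the post-baseline value minus the baseline value, and "Negative changes from baseline indicate improvement". Where a patient has not come from an earlier study of the drug, the rule is: "baseline modified Himmelsbach values will be defined as the latest non-missing value collected prior to the first dose of study drug in this study". That value may come from screening or from Visit R1. For rollover patients the primary baseline uses the same latest-non-missing principle, applied to the earlier pivotal study.

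Section 6.3.1 lists the composite among the safety variables: "Observed values and change from baseline in composite score in modified Himmelsbach scale for the evaluation of centrally mediated opioid withdrawal symptoms". Section 6.3.14 names opioid withdrawal as a specific topic of interest. Section 12.2.1 summarizes the composite descriptively by arm. Section 12.2 plans outlier analyses and names this scale, with criteria to be settled before database lock.

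The protocol contains no proration, item-mean scoring or imputation for a composite with one or two signs missing.

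**The concern.** A tolerance for missing items normally goes with a step that restores the score to its full scale. Section 11.1.5 supplies the tolerance but not that step. If the definition is programmed as it stands, the sum runs over the rated signs only, and an unrated sign has the same effect as a sign rated 0 (none). A composite built on six or seven signs is then reported, and subtracted, on a scale meant for eight.

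What is at stake is the reading of a withdrawal measure in a study whose purpose is safety. A patient with real signs could fall below an outlier cut-off because one or two signs were not recorded. A change score could also reflect how many signs were rated rather than how the patient was. The baseline rule adds a further route: a partial composite at Visit R1 counts as non-missing and could displace a complete screening composite.

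**Working it through.** **Inputs.** Eight signs, each 0 to 3 (Section 6.3.8). Plain sum, composite set to missing above 25% missing, change = post-baseline minus baseline (Section 11.1.5).

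**The plan's own figure.** 8 × 3 = 24, which reproduces the stated range of 0 to 24.

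**Which scores are retained.** With m signs missing, the missing share is m/8, the maximum of the plain sum is 3 × (8 − m), and the largest possible understatement is 3 × m.

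| m | m/8 | Composite | Maximum sum | Largest understatement |
|---|---|---|---|---|
| 0 | 0% | kept | 24 | 0 |
| 1 | 12.5% | kept | 21 | 3 |
| 2 | 25.0% | kept | 18 | 6 |
| 3 | 37.5% | set to missing | – | – |

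No sign can score below 0, so leaving one out never raises the sum. The observed composite can be too low but not too high.

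**Direction of the change score.** If only the post-baseline rating is incomplete, the change is shifted by 0 to −6 points. If only the baseline is incomplete, it is shifted by 0 to +6 points.

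**Unchanged patient, every sign mild (illustration).** The true composite is 8 at both visits. With one post-baseline sign missing the sum is 7 and the change −1. With two missing the sum is 6 and the change −2. Prorated, 7 × 8/7 = 8 and 6 × 8/6 = 8, so the change is 0 in both cases.

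**Patient who worsens by one point (illustration).** Baseline signs are 1, 1, 1, 1, 0, 0, 0, 0 (sum 4). Post-baseline signs are 2, 1, 1, 1, 0, 0, 0, 0 (sum 5). Two post-baseline signs are missing at random, giving 28 possible pairs.
- The mean plain sum is 5 × 6/8 = 3.75, so the mean change is −0.25 against a true +1.
- The sum falls below 4 in the 7 pairs that include the sign scored 2 and in the 3 pairs drawn from the three signs scored 1. That is 10 of 28 (36%) showing apparent improvement.
- The mean prorated sum is 3.75 × 8/6 = 5, so the mean change is +1.

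**Effect on an arm mean.** Let f be the share of visits with two signs missing at random and M the mean true composite. The mean falls by f × M × 2/8. The documents give neither input, so these are assumed ranges: f from 1% to 10% and M from 0.5 to 4.
- Low end: 0.01 × 0.5 × 0.25 = 0.00125 points.
- High end: 0.10 × 4 × 0.25 = 0.10 points.

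**Where proration errs.** In the baseline profile above (true 4), suppose two signs that are truly 0 go unrated. The plain sum is 4, which is correct. Proration gives 4 × 8/6 = 5.33, an overstatement of 1.33.

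**The case against.** The strongest reply is that Section 11.1.5 never says an unrated sign counts as 0. It is silent on one or two missing signs, and a 0 to 24 range at each visit fits a rescaled score at least as well as a truncated one. Section 12.2 promises a comprehensive SAP before database lock, which could add proration. This stands in part: counting as zero is the literal result of the sum, not a stated rule. But the protocol did not leave item-level missingness to the SAP. It wrote the threshold itself, and following that text as written gives an inferior score.

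The other objections concern size, and they largely stand.
- Exclusion criterion 8 (Section 4.2) keeps out patients who, at randomization, have signs the investigator attributes to opioid withdrawal. Section 1.1 reports no central withdrawal symptoms in Phase II. Scores should therefore lie near 0, where an unrated sign is most likely a true 0 and a plain sum is nearly unbiased.
- Raters are trained and certified (Section 6.3.8), and missing data are queried (Section 10.2), so partial ratings should be uncommon.
- There is no statistical testing, and withdrawal is also examined through adverse events identified before lock (Section 12.2.1).

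A reader might go further and infer that the protocol prescribes a score biased toward improvement. The documents do not support that. Only the observed composite errs in a single direction; the change score can err either way, depending on which visit is incomplete. Nothing indicates that partial ratings would differ between arms.

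**Conclusion.** The point holds as a minor one. The protocol fixes a plain sum and a tolerance of up to two unrated signs, and omits the step that would make a retained score comparable with a complete one. Read literally, a retained composite is capped at 21 or 18 instead of 24 and can be low by as much as 3 or 6 points. The 6-point case requires both unrated signs to be severe, which is a bound and not an expectation.

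For arm means the likely effect is about 0.001 to 0.10 points on the 24-point scale. This rests on the assumed ranges for partial ratings and mean score, and on signs being missing at random. It would be misleading to infer that the comparison of arms on withdrawal is materially distorted. The practical exposure is in individual change scores and in the planned outlier analysis, where a few points on one patient can matter.

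**What to change.** In Section 11.1.5, after the sentence on missing signs, add that when one or two signs are missing the composite equals the sum of the rated signs × 8 / the number of rated signs. State that the same rule applies at baseline and at every post-baseline visit, including baselines taken from the earlier studies. Keep the rule that more than 25% missing gives a missing composite. Set the outlier criteria knowing that prorated scores may not be whole numbers.

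The cost is one sentence and one line of code, with no change to data collection, and it can be settled before database lock. The downside is that proration assumes the unrated signs resemble the rated ones, so a score may be slightly overstated when they are truly 0. Requiring all eight signs would avoid that assumption, but it would discard ratings that the present rule keeps.
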